Our team has been working on SSB-related behaviors in Appalachia for over 8 years. We have recently conducted a systematic literature review on youth SSB interventions and a feasibility study of Kids SIPsmartER in one Appalachia middle school. Adapted from our evidence-based SSB reduction program for Appalachian adults, Kids SIPsmartER is grounded by the Theory of Planned Behavior as well as health literacy, media literacy, numeracy, and public health literacy concepts. In our Kids SIPsmartER feasibility study we found significant improvements in SSB behaviors, media literacy and public health literacy among middle school students. Also, students and teachers found Kids SIPsmartER acceptable, in-demand, practical, and implementable within existing school resources. For this R01, Kids SIPsmartER will be a 12 session, 6-month program with an integrated two-way short service message (SMS) strategy to engage parents/guardians in SSB role modeling and supporting home SSB environment changes. Our data from the targeted counties indicate approximately 76-82% adults use SMS. Our SMS message bank will be adapted from our current interactive voice response system that has 102 SSB reduction strategies, specific to 14 barriers identified specifically for this region through formative and qualitative research phases.

Our study is guided by the RE-AIM (reach, adoption, effectiveness, implementation, maintenance) framework, which enables evaluation at the individual-level (i.e., student and parents/guardians) and organization-level (i.e., teachers and schools). Our cluster-randomized controlled trial targets 12 middle schools in medically underserved, Central Appalachian counties in Virginia. Specifically, our proposed R01 is a type 1 hybrid design with a primary aim of evaluating effectiveness among 7th grade students and with secondary aims of exploring caregiver outcomes and implementation factors among teachers and schools. In each school's first year of implementation, Kids SIPsmartER will be co-delivered by researchers and ~24 teachers. In the school's second year of implementation, teachers will be trained and supported to deliver Kids SIPsmartER with reduced in-class support. We anticipate enrolling ~3420 students and ~3180 parents/guardians.

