**Study Logistics** This study began in the 2018-19 school year and will run for 7 years. All human subjects will come from 12 middle schools. To be eligible for the study, schools should be in the geographical Central Appalachia catchment area in southwest Virginia, have approximately 80 to 200 students in the 7th grade, and have an 8th grade within the same school building. The latter eligibility criteria is in effort to promote student retention at the 19-month data point. We have identified at least 22 schools that meet this criteria. If more schools are needed, we can also extend our catchment area in Central Appalachia, including to qualified schools in West Virginia.

A key intent of our design is to allow schools equal opportunity to benefit, regardless of randomized treatment allocation. For pragmatic reasons, we are not proposing a simple randomization approach in which all 12 schools (clusters) are randomized at the out-set of the study. Due to turnover in administration/teachers and fluctuations in resources, our school informants indicated it is unrealistic for a school to enter into an agreement for a research project that is as far as 3-4 years out. Therefore, to promote sound randomization and school retention, we propose to recruit and randomize 4 schools [2 Intervention Schools (IntS) and 2 Control Schools (ConS)] in 3 separate blocks. Among Intervention Schools (IntS), both students and parents complete the evaluation components and receive Kids SIPsmartER. In Control Schools (ConS), both students and parents only complete the evaluation components, they do not receive the Kids SIPsmartER program. Control schools become Delayed Intervention Schools (DIntS) schools in the following academic year and receive the Kids SIPsmartER program (See Attachment in Study Overview file).

[MODIFICATION August 10 2021]: Throughout the execution of in-person study activities, researchers will abide by current UVA policy regarding masks as well as any school-level policies that exceed UVA policy.

Within each block of our stepped wedge design, we will use pure randomization. IntS and Delayed Intervention Schools (DIntS) are co-delivered by researchers and 7th grade teachers, whereas Support Schools (SupS) and Organizational Maintenance (OrgM) School are delivered by 7th grade teachers. Student and caregiver individual-level data is collected during IntS, DIntS, ConS and

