**Describe the participants in this group.**

Students (IntS, DIntS, SupS, SupS2) 7th grade students in the 12 enrolled schools during the years their school is randomized to one of these cohorts are eligible to participate. Parents/guardians agreeing to participate in the texting component is not an eligibility requirement for students to participate. Based on average number of students per school (n=133) and consenting rates from past work in the region (86%), we anticipate that 114 students per school will participate in each cohort for a total of 4218 students. Of these students, 3420 will take part in the NIH funded portion of the trial, with 2736 taking part in both data collection and curricular activities as part of Intervention, Delayed Control, and Supported cohorts and another 684 will participate in data collection activities without receiving Kids SIPsmartER as part of Control cohorts. Within the Virginia Foundation for Healthy Youth funded Continued Support cohorts, 798 students will participate.

Data from students with major cognitive disabilities that could compromise self-report behavioral data quality will also be excluded; we will rely on information provided by the teachers to make this decision.

Students (focus group subset)

The research staff will work with classroom teachers in intervention, delayed intervention, and support schools to identify ~20

students across their classes to join the focus groups. Considerations when selecting students will include limiting disruption to the school day and selecting students who it is anticipated will be able to contribute to group discussion.

**Will participants in this group be compensated for taking part in your study?** No

**Participant Group Name:** Teacher & Principals

**Age Range (years):** >18 years

**Vulnerable populations:** no vulnerable population (none)

**Maximum number of participants, in this group, expected to enroll over the life of the study:** 36

**Minimum number of participants, in this group, expected to enroll over the life of the study:** 0

**Total number of participants, in this group, ever enrolled:** 8

**Approximate number of participants, in this group, currently enrolled:** 8

**Future Enrollment:** We will enroll participants, in this group, during the next twelve months

**Approximate number of participants, in this group, expected to enroll in the next twelve months:** 8

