### Power calculation and sample size

Given the lack of interventions and designs similar to Kids SIPsmartER, data from the Kids SIPsmartER feasibility study were used to estimate the effect size and intraclass correlation (ICC) of students' SSB intake. Considering the school size eligibility criteria and anticipated variation in the number of students per school (range 80-200 students, average 133 students), a lower and upper range of power is estimated. Due to the cluster-randomized block design (i.e., randomization at school level), no attrition at the school level is anticipated. The sample size calculations are conservatively based on a small 7-month effect size of 0.3, a 0.05 type I error, and a 0.01 ICC of students' SSB intake. To achieve 80% power under these assumptions, a total of 12 schools/clusters (6 schools per condition) are needed, with 54 enrolled students per school (and 49 retained after an anticipated 10% attrition rate at student level at 7-month). Following these same assumptions, 99.99% power would be achieved with a total of 12 schools/clusters and an average of ~115 students enrolled per school (and 104 retained after an anticipated 10% attrition rate). In sum, using conservative effect size and ICC estimates and standard type I error rate, enrolling a minimum of 54 students and up to 115 students per 12 schools/clusters would provide adequate power ranging from 80% to 99.9% for the primary 7-month SSB student outcome.

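### The 0.01 ICC is credited to a one-school feasibility study, its level is not stated and no basis is given for calling it conservative; power at planned enrolment recomputes to about 90–96%, not 99.9%

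*SAP*

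**What the plan says.** The SAP, Power calculation and sample size, names one source for its inputs: "data from the Kids SIPsmartER feasibility study were used to estimate the effect size and intraclass correlation (ICC) of students' SSB intake". The calculation then uses an effect size of 0.3, a type I error of 0.05 and "a 0.01 ICC of students' SSB intake", with six schools per condition. Two school sizes are considered:

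- 54 enrolled and 49 retained per school, with stated power 80%.
- About 115 enrolled and 104 retained per school, where "99.99% power would be achieved with a total of 12 schools/clusters".

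The closing sentence describes this as "using conservative effect size and ICC estimates" and says that the enrolment range "would provide adequate power ranging from 80% to 99.9" per cent. The upper figure therefore appears both as 99.99% and as 99.9%. Only school size varies; the ICC stays at 0.01.

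The protocol's Study Overview describes the earlier work as "a feasibility study of Kids SIPsmartER in one Appalachia middle school". Its Study Logistics section says the plan is to "recruit and randomize 4 schools [2 Intervention Schools (IntS) and 2 Control Schools (ConS)] in 3 separate blocks". In the Students group description, "we anticipate that 114 students per school will participate in each cohort", which is the SAP's upper scenario in practice.

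The SAP's Primary effectiveness aim models heterogeneity at student, class and school level and includes block fixed effects. Its Data analysis section says the eligible schools are alike in income and race; no ICC figure is attached to that remark.

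**The concern.** Schools are the randomised units, so the variance of the treatment comparison depends on the share of variance lying between schools. A study in one school can show how much classes differ within it, but not how much schools differ. If 0.01 came from those data it is a class-level or some other within-school quantity. If it is meant as a school-level value, it is an assumption presented as an estimate.

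The label conservative also needs support. A smaller ICC gives more power, so 0.01 lies in the favourable direction unless there is reason to expect less. Similarity in income and race is a qualitative reason to expect a small ICC, but it is not an estimate for beverage intake.

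At stake is how the power statement can be read. It rests on one value of its least supported input, with no sensitivity shown, and its upper figure looked too high for 12 schools. A reader interpreting a null result, or planning a later school trial from this SAP, would take the design to have more margin than the inputs give.

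**Working it through.** **Inputs.** From the SAP power section: effect d = 0.3; ICC ρ = 0.01; k = 6 schools per arm; m = 49 or 104 retained per school; α = 0.05. Sidedness is not stated and is taken as two-sided; one-sided results are given below. ρ is read as school-level. Schools are taken as equal in size, with no gain from baseline adjustment, because the power section claims none.

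**Formulas.** Design effect DE = 1 + (m − 1)ρ. SE = √(2·DE/(k·m)). Noncentrality λ = d/SE. Power is taken from the normal, and from the noncentral t with 10 df (12 schools less 2 arms) and 8 df (also less 2 block terms).

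**Reproducing the stated figures at ICC 0.01.**

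- m = 104: DE = 1 + 103 × 0.01 = 2.03; SE = √(4.06/624) = 0.0807; λ = 3.72. Power is 96.1% (normal), 91.7% (t, 10 df), 90.1% (t, 8 df). Stated: 99.99% or 99.9%.
- m = 49: DE = 1.48; SE = √(2.96/294) = 0.1003; λ = 2.99. Power is 84.8, 76.9, 74.5%. Stated: 80%. The nearest match is 79.4%, with 54 analysed (before attrition) and t on 10 df.

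**Looking for a reading that gives both stated figures.**

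- One-sided, normal: 98.1% at 104, but 91.1% at 49.
- 115 analysed instead of 104: 96.8% (normal, two-sided).
- ICC 0, two-sided normal: 99.96% at 104, but 95.3% at 49.
- Class-level ICC of 0.01 with no school variance, assuming 20–25 students per class (normal, two-sided): 99.7–99.8% at 104, but 90–92% at 49.
- Baseline correlation 0.7 (assumed), ICC 0.01, normal: 99.94% at 104, but 98.7% at 49.
- Any school size: as m grows, SE tends to √(2 × 0.01/6) = 0.0577, so λ cannot exceed 5.20 and power cannot exceed 99.94% two-sided (99.98% one-sided), without baseline gain.
- Any effect size: 80% at 49 needs λ = 2.80 (normal, two-sided). Going to 104 multiplies λ by at most √(104/49) = 1.457, reached at ICC 0. That gives λ = 4.08 and power 98.3%. The two stated figures therefore conflict with each other.

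**Sensitivity to the ICC.** The range is illustrative and is not evidence of the true value. Power (%) is normal / t 10 df / t 8 df, two-sided:

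| ICC | 49 retained | 104 retained |
|---|---|---|
| 0.01 | 84.8 / 76.9 / 74.5 | 96.1 / 91.7 / 90.1 |
| 0.02 | 73.8 / 65.0 / 62.6 | 85.8 / 77.9 / 75.6 |
| 0.03 | 64.4 / 55.7 / 53.5 | 74.5 / 65.7 / 63.3 |
| 0.05 | 50.5 / 43.0 / 41.2 | 57.0 / 48.8 / 46.8 |
| ICC at which power is 80% | 0.0143 / 0.0077 / 0.0061 | 0.0250 / 0.0185 / 0.0169 |

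With an assumed baseline correlation of 0.5 (variance multiplied by 1 − 0.25 = 0.75), the 80% thresholds, now for the residual ICC, become 0.026 / 0.017 / 0.015 at 49 and 0.037 / 0.028 / 0.026 at 104. Unequal school sizes, with an assumed coefficient of variation of 0.25 and DE = 1 + ((1 + 0.25²)m − 1)ρ, lower power at ICC 0.01 by about one point or less.

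The effect detectable with 80% power at 104 retained is 0.23 / 0.25 / 0.26 at ICC 0.01, 0.28 / 0.31 / 0.32 at 0.02, and 0.39 / 0.44 / 0.45 at 0.05.

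**The case against.** The 90–96% depends on conditions that the SAP does not state: a school-level ICC, a two-sided test and no baseline gain. Read as a class-level ICC with a one-sided test, power at 104 is 99.91–99.93%, which is the stated 99.9%; one-sided at ICC 0 it is 99.987%, which rounds to 99.99%. This is fair, and the conditions must travel with the figure. But those readings give 94.8–95.4% and 97.7% at 49, not 80%, so the mismatch remains.

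The planned model controls effects that are fixed over time, so stable differences between schools are at least partly removed and a post-only calculation may understate power. With an assumed correlation of 0.5 and ICC 0.02, power at 104 is 93.8 / 88.2 / 86.4%. This also stands, and is why the thresholds are given both ways; the power section itself claims no such gain.

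The documents prescribe no t reference, and the 8-df column deducts block terms without crediting any between-block variance removed. That is also fair: the t columns are a reviewer's choice, shown beside the normal result. The normal figure of 96.1% already falls short of 99.9%.

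The case of 49 retained is unlikely. A school of 80 with the protocol's 86% consent and 10% attrition retains about 62 (80 × 0.86 × 0.9), where power at ICC 0.01 is 89.7 / 82.7 / 80.6%. True, but the SAP presents 54 enrolled as an adequate minimum, so its figure should be correct.

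Finally, 0.01 may have been set above whatever the feasibility report found. This review has no access to that report and makes no claim about its value. Whatever it was, one school could not have yielded a between-school ICC.

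**Conclusion.** The concern holds. The named source cannot supply a school-level ICC, the level of the 0.01 is not stated, and the documents give no basis for calling it conservative at the level of randomisation. Separately, even if 0.01 is right, the upper power figure is about 90–96% rather than 99.9% or 99.99%, assuming a school-level ICC, a two-sided test, equal school sizes and no baseline gain. No reading tried gives both stated figures.

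This does not show that the trial is underpowered or that the true ICC exceeds 0.01, and the effect size of 0.3 is not challenged. At 104 retained, power stays above 80% up to an ICC of about 0.017–0.025. At 49 retained the room is small (up to 0.014) under the normal, and there is none under either t reference, where power at 0.01 is already 74.5–76.9%. The SAP text should be corrected; the conduct of the trial is not affected.

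**What to change.** In the SAP, Power calculation and sample size:

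1. State which level the 0.01 describes. Present the school-level ICC as an assumption, or cite a source with several schools.
2. Remove the label conservative from the ICC, or give its basis at school level. The effect size wording can stay.
3. Replace the 99.99% figure and the 80% to 99.9% range with power recomputed over an illustrative ICC range of 0.01–0.05 at 49 and 104 retained. State sidedness, the reference distribution, the degrees of freedom including blocks, and any baseline gain assumed.
4. As an optional addition to the report, give the trial's own school-level ICC for SSB intake with block effects removed and a 95% confidence interval, noting that a raw baseline ICC is not the residual ICC of the primary model. The interval will be wide: an estimate of 0.01 with 104 per school and 9 between-school df (12 schools less 3 blocks) has an F-based interval of about 0 to 0.053.

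The cost is a few sentences, one short table and, if item 4 is taken up, one reported estimate. Enrolment, estimand and analysis model do not change; the protocol dates completion of the primary outcome to May 2021. The drawback is a less favourable stated power.

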#### ***Primary effectiveness aim***

Multi-level mixed effect models will be used to control errors of non-independence and heteroscedasticity caused by individual, class and school heterogeneity, and potential covariates identified a priori based on the literature and theory that are relevant to SSB behavior changes. The treatment effect models used in this study will contain outcomes of interest as dependent variables (e.g., SSB kcal, quality of life measures etc.). Specific mixed effect link function will be chosen to fit different outcome distributions. The models will control those unobserved effects that are fixed over time at three different levels (i.e., individual student, class, and school) and

those unobserved time and block fixed effects that are individual-class-school-invariant. To further examine intervention treatment effect differences across blocks, we will modify the models to allow group indicator to interact with time-block fixed effects.

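### The SAP's upper power figure (99.99%, then 99.9%) does not follow from its own inputs, which give about 92% to 96% for a two-sided test

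*SAP*

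**What the plan says.** The SAP section on power and sample size bases its calculation on "a small 7-month effect size of 0.3, a 0.05 type I error, and a 0.01 ICC", with 12 schools, six per condition, and no loss of schools. It gives two scenarios:

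- **Lower:** 54 students enrolled and 49 retained per school, for 80% power.
- **Upper:** under the same assumptions, "99.99% power would be achieved with a total of 12 schools/clusters and an average of ~115 students enrolled per school", with 104 retained after 10% attrition.

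The closing sentence says that enrolment across this range "would provide adequate power ranging from 80% to 99.9% for the primary 7-month SSB student outcome". The section does not state whether the test is one- or two-sided, which formula was used, or the reference distribution and its degrees of freedom.

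Three other places bear on the figure. The Protocol (Study Logistics) says that eligible schools should "have approximately 80 to 200 students in the 7th grade". The Protocol's description of the student group says "we anticipate that 114 students per school will participate in each cohort". The SAP's primary effectiveness model includes "those unobserved time and block fixed effects that are individual-class-school-invariant".

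**The concern.** The same scenario is given 99.99% power in one sentence and 99.9% in the next. These imply type II errors of 0.01% and 0.1%, a tenfold difference.

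Both values also look too high for the design. With only six schools per arm, between-school variation limits what extra students per school can add. Going from 49 to 104 retained students roughly doubles the sample, but at ICC 0.01 the effective sample grows by only about half.

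This is the SAP's only power statement for the primary 7-month outcome. A reader would take the risk of missing a true effect of 0.3 to be negligible, and has no stated method against which to check that.

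**Working it through.** **Inputs, all from the SAP power section:** effect size d = 0.3 (SD taken as 1), type I error 0.05, ICC 0.01, k = 6 schools per arm, m = 49 or 104 retained students per school. Sidedness is not given. Two-sided is assumed and one-sided is shown as well.

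**Formulas**

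- Design effect: DE = 1 + (m − 1) × ICC
- Effective students per arm: n = k × m / DE
- Noncentrality: ncp = d × √(n / 2)
- Power: normal approximation, or noncentral t with 10 df (12 schools minus 2 arms). An 8 df version assumes that three blocks use 2 further df.

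**Lower scenario first (m = 49; the SAP states 80%)**

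- DE = 1 + 48 × 0.01 = 1.48
- n = 294 / 1.48 = 198.6
- ncp = 0.3 × √(198.6 / 2) = 2.990

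Two-sided power is 84.8% (normal), 76.9% (t, 10 df) or 74.5% (t, 8 df). The stated 80% lies within this range, so it is treated as approximate and not as an error.

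**Upper scenario (m = 104; the SAP states 99.99% and 99.9%)**

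- DE = 1 + 103 × 0.01 = 2.03
- n = 624 / 2.03 = 307.4
- ncp = 0.3 × √(307.4 / 2) = 3.719

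| Method | Two-sided | One-sided |
|---|---|---|
| Normal | 96.1% | 98.1% |
| t, 10 df | 91.7% | 96.5% |
| t, 8 df | 90.1% | 95.9% |

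Ignoring attrition (m = 115) gives 96.8% (normal) or 92.8% (t, 10 df), two-sided.

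**Ceiling.** As m grows without limit, n tends to k / ICC = 600 and ncp to 0.3 × √300 = 5.196. Power then tends to 99.94% (two-sided normal), 99.98% (one-sided normal) or 99.6% (two-sided t, 10 df). So 99.99% is out of reach at any school size.

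**What 99.9% would need (two-sided normal).** Either about 1,690 analysed students per school at ICC 0.01, or an ICC of about 0.001 at m = 104. At the eligibility limit, with all 200 students analysed, power is 98.9% (normal) or 96.8% (t, 10 df).

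**Could an unstated method explain both ends?** Take the SAP's 80% at m = 49 as given and scale the noncentrality to m = 104. At ICC 0.01 the ratio is 3.719 / 2.990 = 1.244. For the two-sided normal test, 80% corresponds to ncp 2.802, which becomes 2.802 × 1.244 = 3.485, or 93.6% power. The t versions give 93.5%, and one-sided versions 92.5% to 92.6%. The largest possible ratio, with no clustering, is √(104 / 49) = 1.457, and power is then at most 98.3%. So a method whose precision gain is the same in both scenarios cannot match both ends of the stated range.

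**ICC set to 0.** At m = 104 this gives 99.96% (two-sided normal) or 99.987% (one-sided normal), close to the stated figures. The same setting gives 95.3% two-sided at m = 49, not 80%.

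**The case against.** The best counter-argument concerns weight. The SAP concludes only that power is adequate, and at 104 retained it exceeds 90% by every method above. The Protocol describes the primary 7-month outcome as completed by May 2021, so a corrected sentence can hardly change a design decision. That stands, and it limits the practical effect. It does not make the figure correct.

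Second, the recomputed values rest on a simple two-level model. The SAP plans student, class and school levels with covariates, and states no power method. The 8 df version in particular is an assumption, and it alone produces the 10-point end of the gap. This too stands, and it is why the fix asks for one declared method. But covariate gains cannot rescue the upper figure: anchored to the SAP's own 80% at 49 retained, power at 104 is at most 98.3%.

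Third, 99.9% may simply be 99.99% with a digit dropped, and the near-match at ICC 0 suggests that clustering may have been left out of the upper calculation. Both are plausible, but the documents say neither. If clustering was omitted, that would confirm the error, because the SAP says that both scenarios use the same assumptions.

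**Conclusion.** The concern holds. On the SAP's own inputs, two-sided power at 104 retained students per school is 96.1% (normal) or 91.7% (t, 10 df), against a stated 99.99% and 99.9%. The overstatement is about 4 to 8 percentage points, or 10 with 8 df. One-sided, it is about 2 to 3.5 points.

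Put as the risk of missing a true effect of 0.3, the SAP implies 0.01% to 0.1%, while its inputs give about 4% to 10% two-sided.

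The exact size depends on sidedness and degrees of freedom, which the SAP leaves open. The conclusion does not: none of these choices reaches 99.9% at 104 retained with ICC 0.01, and 99.99% is above the ceiling for six schools per arm. The trial is not underpowered at its planned size on these inputs. The stated power is wrong and its method cannot be checked.

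**What to change.** In the SAP power section, delete 99.99% and 99.9%. State the sidedness, the formula and the degrees of freedom, and give the power of both scenarios by that one method. For a two-sided 0.05 test the entries would be:

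| Retained per school | Normal | t, 10 df | t, 8 df |
|---|---|---|---|
| 104 | 96% | 92% | 90% |
| 49 | 85% | 77% | 75% |

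If a t reference is chosen, add that 80% power needs about 56 (10 df) or 61 (8 df) analysed students per school, so that the lower scenario is described by the same method.

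The cost is SAP wording and a less favourable stated power. No endpoint, analysis, number of schools or enrolment target changes, because the Protocol already expects 114 participants per school in each cohort.
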